**Table 1. Data Collection for Specific and Secondary Aims**

Measure	Visit 1 Baseline Randomization	Visit 2 Week 12	Visit 3 Week 24	Visit 4 Week 36	Visit 5 Week 48
Mediators					
Self-efficacy	x	x	x	x	x
Appointment keeping	x	x	x	x	x
Adherence	x	x	x	x	x
Satisfaction with communication	x	x	x	x	x
Navigating ability	x	x	x	x	x
Moderators					
Educational attainment	x				
Baseline health literacy (ANQ, S-TOFHLA)	x				
Socio-demographics	x				
Comorbidities*					
Community factors (ECV)	x				
Affective State: Anxiety/Depression	x				
Clinician characteristics	x				
Participant Outcomes					
Asthma Control	x	x	x	x	x
Prednisone bursts, ED, hospitalizations	x	x	x	x	x
Asthma-Related Quality of Life (AQOL)	x	x	x	x	x
Spirometry (FEV1, FVC)	x	x	x	x	x

\*Comorbidities include diabetes, hypertension, obesity, cancer, smoking history, and other conditions as reported by participant and verified in the medical record. ANQ= Asthma Numeracy Questionnaire, S-TOFHLA= Short Test of Functional Health Literacy in Adults, ECV= Exposure to community violence.

**D.3. Subjects: Inclusion criteria** for 300 subjects (1-5 also of the HAP Study) are: 1)  $\geq 18$  years of age, 2) physician's diagnosis of asthma, 3) prescribed an inhaled-steroid-containing medication for asthma (ensuring the patient is believed to have moderate or severe reversible airways obstruction by their physician), 4) moderate or severe persistent asthma according to the NHLBI Guidelines, 5) evidence of reversible airflow obstruction: (a) forced expiratory volume in 1 second (FEV1)  $< 80\%$  predicted at the time of screening or within the 3 years prior to this screening, and (b) improvement with bronchodilator: either (i) an increase of  $\geq 15\%$  and 200ml in FEV1 with asthma treatment over the previous 3 years or (ii) after 4 puffs of albuterol by MDI (or 2.5 mg by nebulizer), an increase in FEV1 or FVC  $\geq 12\%$  and 200 ml in FEV1 within 30 minutes, and 6) at least one appointment scheduled with the asthma physician during the 1st 6 months of participation.

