## **D.6. Protocol**

**D.6.1. Data Collection Visits** generally occur at a private location in the practice of the participant's asthma provider. (Most providers are physicians; but some are physician trainees (residents, fellows), or nurse practitioners.) After explanation of the protocol, informed consent is obtained and baseline data collected by the DC (Table 1, Fig. 2)). Participants then are randomized (D.2.2) 1:1 to either PAI or UC. As a pragmatic trial, there is no run-in as this would select those most adherent. Except for the test of reading comprehension, questionnaires are read to patients as they look on in English or Spanish as preferred by the participant. All questionnaires and all scripts have been translated into Spanish and independently reviewed by other native Spanish speakers and compared with English versions. Data collection (Table 1) occurs quarterly. All participants are reminded of data collection appointments with a phone call a few days prior to the visit.

At each visit the DC asks participants how they are feeling and about urgent care obtained since the last visit, e.g., ED visits, hospitalizations, new or increased prednisone prescriptions ("prednisone bursts"). From HAP we know there will be 3-5 participant visits with the clinician during the observation period for both PA and UC participants. PA, but not UC, activities surround these visits. Randomization ensures approximately equal numbers of MD visits (which will be tallied) in participants assigned to PA and UC.

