**Table 2: Project Timeline**

Year	1	2	3	4	5										
Months	1-6	7-8	9-12	13-16	17-20	21-24	25-28	29-32	33-36	37-40	41-44	45-48	49-52	53-56	57-60
Start up: finalize IRB approval, finalize CRFs, train staff, create database															
New enrollment	50		100		100		50								
Follow-up															
Data analysis															
Focus groups: set up, conduct, analyze															
DSMB meets	x		x									x			

range of representative rates for those not employed. We will adjust costs for inflation using the Consumer and Medical Price Indices, as appropriate, and discount costs to the base year using a discount rate of 3%.

**D.9. Data Analysis:** We will perform descriptive analyses of all variables, then compare PA and UC groups for the adequacy of randomization, examining if covariates or baseline variables including potential moderators of the intervention and mediating relationships are equally distributed among patient groups. These baseline comparisons will be based on t-tests or Wilcoxon rank sum tests for continuous variables depending on the symmetry of the distributions, on logistic regression for binary or ordinal variables; and on Poisson log-linear regression for count data. If imbalances are found at baseline, the relevant variables will be treated as confounders in the ITT analyses and the analyses of mediators and moderators of the intervention on asthma control. To account for the potential for variation in the effectiveness of the intervention across physician practices, our analyses will compensate by including site as a fixed effect in all analyses. Analyses of PA and UC differences with respect to change from baseline at 6 and 12 months for each outcome in Aims 1 and 2 will be based on the ITT principle: all randomized subjects will be included in the analysis regardless of whether they drop out of the intervention or study. We will perform a sensitivity analysis of the missing at random assumption by following Bruce et al with a non-ignorable shared parameter model.

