The analysis will be based on random effects (RE) models applied to baseline and all follow-up visits at which outcome data are collected. The RE will be included to account for correlated and missing data. Separate time effects and time-treatment interactions will be specified for each follow-up visit, such that the treatment-time interaction for a particular visit will be the ITT effect on change since baseline. The RE models will be linear, logistic, and log-linear for continuous, binary, and count outcomes, respectively. Similar RE models will be employed for assessment of mediation and moderation in Secondary Aims 1 and 2.

**Data description, screening, and reorganization:** We will screen data for quality and integrity as proposed by Altman. For all variables we will determine measures of central tendency: mean and standard deviation for continuous variables, median and range for categorical variables. We will examine frequency distribution graphically (histograms, scatter plots) for all variables. Specific concerns will be directed to understanding the pattern of missing values, isolating outliers, confirming the homoscedasticity of observation groups, verifying the coding consistency, examining adherence to normality for variables anticipated to be so, and locating normalizing transformations for continuous variables intended to be investigated as such. For the tools we developed, we will examine internal consistency using Cronbach's  $\alpha$ .

**Addressing the impact of site on each outcome:** First, we will pool participants across sites, assuming no site effect, using logistic and regression modeling to isolate the relationship between outcome and exposure and other demographics. We have stratified randomization to analyze the effect of site. We have amplified the sample size (D.10) to have a large enough sample to conduct this analysis. As a secondary analysis, we will examine treatment-site interactions. In the presence of statistically significant interactions, we will present separate estimates of treatment effects for each site. In the case of statistically, but clinically marginally significant interactions, we will present main effect estimates of treatment effect but with interactions in the model using -1, 0, 1 dummy coding for site, so that the main effects' estimates will be for the average site.

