**D.13. Timeline** is summarized in Table 2. Some staff is already identified and trained. We have established relationships at recruitment sites and successful recruitment strategies. The MOP of HAP needs minor modifications. HAP case report forms require small modifications.

**D.14. Anticipated problems:** Insuring recruitment/retention: We will use our successful procedures, using electronic medical records, and relationships developed with practices. We obtain contact information, e.g., cell phone, address, for 3 contacts per participant. Incentives will be given for each DC Visit with the largest at the final visit. We flexibly accommodate meeting times for the convenience of participants. RCs will be diverse, reflecting participant demographics. Guaranteeing a culturally appropriate intervention: RCs will undergo formal training. Co-investigators are also diverse and will in observation of the protocol and in staff meetings guarantee a culturally appropriate approach. Standardizing delivery of PA will be accomplished by the use of procedure manuals; standardized, well-annotated, and carefully constructed case report forms; regular direct observation; and audio-taping of researcher interactions with participants. Assuring physicians do not treat UC participants like PA participants: Physicians will not know which of their patients, if any, are enrolled in the UC arm, only those in PA. Almost all of the intervention takes place between PA and patient or is PA-related so it is unlikely to result in change of provider behavior in the absence of a PA. DCs will ask all subjects post-study if they noted changes in their physician over the study period. Post-study focus groups should add support to this claim. Differences in the impact of the intervention between specialty and primary care practices: will be explored in post-intervention focus groups and in the quantitative analysis of outcomes and mediators.

**D.15. Summary:** This RCT disseminates and implements the PAI to improve asthma outcomes in primary care and specialty practices, in an academic health center, a federally qualified health center, a VA and in English- and Spanish-speaking practices, testing its effectiveness, sustainability, and cost-effectiveness. The real-world individualized PAI is compared to usual care, crafted for a vulnerable population, considers patients' unique contexts, social barriers, and comorbidities and is generalizable to many diseases and medical settings.

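### Event counts are collected over a variable interval, but the count model states no exposure offset and no rule for a count taken after a missed visit

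*Combined protocol and SAP*

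**What the plan says.** Section D.6.1: "At each visit the DC asks participants how they are feeling and about urgent care obtained since the last visit". It names ED visits, hospitalizations and new or increased prednisone as examples. The same section says "Data collection (Table 1) occurs quarterly", and Table 1 puts the visits at weeks 0, 12, 24, 36 and 48 (the first follow-up is headed "Visit 2 Week 12"). The nominal interval is therefore 12 weeks, while the actual interval is whatever separates two attended visits.

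Section D.9 gives the models: "The RE models will be linear, logistic, and log-linear for continuous, binary, and count outcomes, respectively". On time it says "Separate time effects and time-treatment interactions will be specified for each follow-up visit", and the interaction at a given visit is the treatment effect on change since baseline. The 6-month interaction is the main test for Aims 1 and 2. The 12-month interaction tests whether the effect persists once the intervention has stopped.

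On missing data, D.9 says "The RE will be included to account for correlated and missing data" and "We will perform a sensitivity analysis of the missing at random assumption", the latter through a shared parameter model. Section D.8.1 has data collectors look for supporting documentation in medical records. It does not say that event dates are recorded or that events are allocated to visit windows. No section mentions an offset, person-time or interval length for any count model.

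**The concern.** A log-linear model without an exposure term compares mean counts per row. That is a comparison of rates only if every row at a visit covers the same length of time, and here a row recorded after a missed visit covers at least twice the nominal time. The stated missing-data methods do not help: they deal with outcomes that were not observed, whereas this row is observed and simply covers too long a period.

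Two things are at stake. First, if the arms differ in how often visits are missed, the rate ratio is biased for three of the five Aim 2 outcomes. Second, a participant who misses Visits 3 and 4 brings events from weeks 12 to 48 to Visit 5. Events from the last 12 weeks of the intervention then count in the contrast meant to describe the period after it. This second problem does not need unequal attendance.

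**Working it through.** **The plan's own figure.** The only stated figure covering these outcomes is the Aim 2 detectable effect in D.10: 0.34 at 6 months and 0.31 at 12 months (80% power, two-sided alpha 0.005, 18% drop-out, intraclass correlation 0.30, 150 per arm).

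- Formula: effect = (z for alpha/2 + z for power) × sqrt(2/n_eff), with n_eff = 150 × 0.82 × k/(1 + 0.30(k − 1)) for k repeated measures.
- k = 3: n_eff = 123 × 3/1.6 = 230.6; effect = 3.649 × sqrt(2/230.6) = 0.340.
- k = 5: n_eff = 123 × 5/2.2 = 279.5; effect = 3.649 × sqrt(2/279.5) = 0.309.

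Both match. The formula has no exposure term, so these figures neither depend on this point nor change with the fix.

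**Possible intervals (Table 1 spacing).**

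| Visit | Nominal weeks | Possible weeks after missed visits |
|---|---|---|
| 3 (6 months) | 12 | 24 |
| 4 | 12 | 24 or 36 |
| 5 (12 months) | 12 | 24, 36 or 48 |

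**Bias at Visit 3.** Let m be the share of Visit 3 attenders in an arm who missed Visit 2, and assume that missing is unrelated to the event rate. The arm's mean count per nominal 12 weeks is rate × [(1 − m) × 1 + m × 2] = rate × (1 + m). Hence apparent ratio = true ratio × (1 + m_PAI)/(1 + m_UC).

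The documents give no value for m. The 18% in D.10 is drop-out, and people who never return add no long count. The rates below are assumptions, with a true ratio of 1:

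| PAI | UC | Apparent ratio |
|---|---|---|
| equal | equal | 1.00 |
| 5% | 10% | 1.05/1.10 = 0.955 |
| 5% | 15% | 1.05/1.15 = 0.913 |
| 5% | 20% | 1.05/1.20 = 0.875 |
| 18% | 10% | 1.18/1.10 = 1.07 |

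**Does exposure time correct it?** Gamma-Poisson counts were simulated with 123 per arm, an assumed 0.3 events per 12 weeks and 2,000 runs. With misses of 5% (PAI) and 18% (UC):

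- true ratio 1.00: 0.89 without exposure time, 0.99 with it;
- true ratio 0.80: 0.72 without, 0.80 with.

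With 10% missed in each arm the two versions agree (0.99 and 0.80).

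**Effect on the test.** A null simulation used 123 per arm, an assumed 0.73 events per year, log variance 0.8 for the patient effect, 20,000 runs and a clustered marginal contrast of change from baseline. At alpha 0.005 the rejection rates were:

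- 5% v 15% missed: 0.65% without an offset, 0.54% with one;
- 5% v 20% missed: 0.72% without, 0.49% with.

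The bias on the log scale is ln(0.913) = −0.09 to ln(0.875) = −0.13, against a standard error of about 0.45.

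**Carry-over into the 12-month contrast.** PAI ends at 6 months (week 24 in Table 1). A Visit 5 count that spans weeks 12–48 contains 12 intervention weeks out of 36, one third. One that spans weeks 0–48 contains 24 out of 48, one half. Missing Visit 4 alone gives weeks 24–48 and no carry-over. An offset rescales such a row but cannot remove the intervention-period events from it.

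**The case against.** The strongest reply is that D.9 is silent rather than wrong. It gives one sentence on link functions for every type of outcome and neither includes nor rules out an offset. A competent analyst might add one, and the record review might supply dates. That stands: the documents do not show a decision to analyse long counts as 12-week counts. This is what follows from fitting the model as described.

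A reader might also infer that UC participants will miss more visits, so that the bias favours PAI. The documents do not establish this:

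- All participants receive a reminder call before data collection visits (D.6.1), and payments and transport tokens apply to both arms (D.6.4).
- The PA's between-visit call is made only after a month without contact (D.6.2), and the intervention stops at 6 months (D.2.2), so PA contact gives no direct reason for unequal misses later.
- HAP is the only source of retention by arm: 3 of 53 PAI and 4 of 47 education participants did not finish (D.1.4). That is drop-out against a different comparator. Read as miss rates, 5.7% and 8.5% would give 1.057/1.085 = 0.97.

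Nor does the D.14 remark "We flexibly accommodate meeting times for the convenience of participants" amount to permission for late visits. It concerns recruitment and retention and sets no visit window. A late visit would also shorten the next interval if that visit were on schedule.

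What survives is the variable recall period, the missing exposure rule and the possible carry-over. Unequal attendance remains plausible during the first 6 months, because only PAI participants have PA contact, but its size and direction are unknown.

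**Conclusion.** The point holds as a gap in specification: the plan states no exposure offset and no rule for counts collected after a missed visit. Its size depends on intermittent-miss rates that the documents do not give. Across the assumed rates the Visit 3 ratio moves from no bias (equal misses) to 0.875 in one direction and 1.07 in the other, assuming that missing is unrelated to the event rate.

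A reader might infer that this would produce false-positive findings. The calculation does not support that: rejection at 0.005 rises only from about 0.5% to about 0.7%. The harm is a biased estimate and a blurred 12-month contrast.

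The ACQ (past-week recall), quality of life and FEV1 are unaffected. D.2.2, D.8.1 and D.10 name asthma control as the primary outcome, although B.7 also lists ED visits and hospitalizations among the primary outcomes. This is a worthwhile, inexpensive improvement and does not threaten the primary analysis.

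**What to change.** In D.9, add log(weeks since the last attended data collection visit) as an offset in the log-linear models for ED visits, hospitalizations and prednisone bursts. State one fixed recall length for everyone at Visit 1, where there is no previous visit to count from.

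On the case report form, record the date of each event during the record check already planned in D.8.1. Where a gap spans a missed visit, assign its events to their 12-week windows, each with its own length as the exposure, so that events before week 24 stay out of the 12-month contrast.

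The cost is a short addition to D.9 and a date field, with no extra visits or participants. The offset needs only visit dates. The window rule needs event dates, which no section says are captured at present, and events that cannot be dated would have to be spread over their gap.

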**Table 2: Project Timeline**

Year	1	2	3	4	5										
Months	1-6	7-8	9-12	13-16	17-20	21-24	25-28	29-32	33-36	37-40	41-44	45-48	49-52	53-56	57-60
Start up: finalize IRB approval, finalize CRFs, train staff, create database															
New enrollment	50		100		100		50								
Follow-up															
Data analysis															
Focus groups: set up, conduct, analyze															
DSMB meets	x		x									x			

range of representative rates for those not employed. We will adjust costs for inflation using the Consumer and Medical Price Indices, as appropriate, and discount costs to the base year using a discount rate of 3%.

**D.9. Data Analysis:** We will perform descriptive analyses of all variables, then compare PA and UC groups for the adequacy of randomization, examining if covariates or baseline variables including potential moderators of the intervention and mediating relationships are equally distributed among patient groups. These baseline comparisons will be based on t-tests or Wilcoxon rank sum tests for continuous variables depending on the symmetry of the distributions, on logistic regression for binary or ordinal variables; and on Poisson log-linear regression for count data. If imbalances are found at baseline, the relevant variables will be treated as confounders in the ITT analyses and the analyses of mediators and moderators of the intervention on asthma control. To account for the potential for variation in the effectiveness of the intervention across physician practices, our analyses will compensate by including site as a fixed effect in all analyses. Analyses of PA and UC differences with respect to change from baseline at 6 and 12 months for each outcome in Aims 1 and 2 will be based on the ITT principle: all randomized subjects will be included in the analysis regardless of whether they drop out of the intervention or study. We will perform a sensitivity analysis of the missing at random assumption by following Bruce et al with a non-ignorable shared parameter model.

The analysis will be based on random effects (RE) models applied to baseline and all follow-up visits at which outcome data are collected. The RE will be included to account for correlated and missing data. Separate time effects and time-treatment interactions will be specified for each follow-up visit, such that the treatment-time interaction for a particular visit will be the ITT effect on change since baseline. The RE models will be linear, logistic, and log-linear for continuous, binary, and count outcomes, respectively. Similar RE models will be employed for assessment of mediation and moderation in Secondary Aims 1 and 2.

**Data description, screening, and reorganization:** We will screen data for quality and integrity as proposed by Altman. For all variables we will determine measures of central tendency: mean and standard deviation for continuous variables, median and range for categorical variables. We will examine frequency distribution graphically (histograms, scatter plots) for all variables. Specific concerns will be directed to understanding the pattern of missing values, isolating outliers, confirming the homoscedasticity of observation groups, verifying the coding consistency, examining adherence to normality for variables anticipated to be so, and locating normalizing transformations for continuous variables intended to be investigated as such. For the tools we developed, we will examine internal consistency using Cronbach's  $\alpha$ .

**Addressing the impact of site on each outcome:** First, we will pool participants across sites, assuming no site effect, using logistic and regression modeling to isolate the relationship between outcome and exposure and other demographics. We have stratified randomization to analyze the effect of site. We have amplified the sample size (D.10) to have a large enough sample to conduct this analysis. As a secondary analysis, we will examine treatment-site interactions. In the presence of statistically significant interactions, we will present separate estimates of treatment effects for each site. In the case of statistically, but clinically marginally significant interactions, we will present main effect estimates of treatment effect but with interactions in the model using -1, 0, 1 dummy coding for site, so that the main effects' estimates will be for the average site.

**Aims 1 & 2 (To assess whether PAI improves asthma control and other asthma outcomes):** The ITT effect of PA relative to UC on change in asthma control and other asthma outcomes since baseline at 6 months will be assessed with estimation and testing of the treatment-6 month visit interaction in the linear RE model (described above) with asthma control as the dependent variable. In addition, the treatment-12 month interaction will be tested and estimated to assess if the ITT effect is retained after the PA intervention ends.

**Secondary Aim 1 (Mediators):** The mediation analysis will follow the 4-step regression approach for testing mediated effects of Holmbeck. First, we will examine the association between PAI and mediators (D.8.2) by fitting separate longitudinal RE models with each mediator as the dependent variable. These models will test the effects of the PAI relative to the UC group with respect to change since baseline at each follow-up visit for the potential mediators. Second we examine the association between the PAI and asthma control as described in Aim 1. Third, we will assess the relationship between the mediators and asthma control by fitting separate longitudinal RE models with the mediators (D.8.2) as the independent variables and asthma control as the dependent variable. Finally, the mediators with significant effects at steps 1 and 3 will be included as a lagged time-varying covariate in the ITT linear RE model for asthma control in Aim 1. Mediators of the PAI will be assessed by comparing the randomization (intervention) effect estimate with and without the potential mediator in the model. A reduction of at least 15% in the treatment-visit interaction parameters at 6 and 12 months due to the inclusion of the mediator in the model will be the criteria for a significant mediator.

**Secondary Aim 2: Moderators** of the intervention (D.8.3) will be tested and estimated with 3- and 2-way interactions among the treatment factor, potential moderator, and visit factor in the ITT model in Aim 1. Similarly, moderators of the mediating relationship will be assessed with 3- and 2-way interactions among the treatment factor, mediator, potential moderator, and visit factor in the mediation model in Secondary Aim 1.

**Specific Aim 3 (To estimate the incremental costs and incremental cost-effectiveness (ICE) of PA):** ICE will be assessed by comparing the incremental cost of PA (including both intervention costs, as well as costs of care) relative to UC per outcome, e.g. cost per day asthma control or avoided ED, hospitalization. The ICE will be determined based on differences in direct costs (payer perspective) and also including indirect

costs (societal perspective) and will be calculated based on differences in mean costs for the UC group from those in the PA group, divided by the mean difference in outcomes (asthma control, prednisone bursts, ED visits, hospitalizations, etc.). We also will calculate the incremental cost per quality adjusted life year as estimated from the AQOL. We will estimate statistical error and construct confidence intervals using bootstrap procedures for the incremental cost difference and the incremental cost-effectiveness ratio (ICER).

**Exploratory Aim (Post-study focus groups of providers):** Audio records and notes will be coded into categories emerging from the data by independent coders ([name], [name], [name]) who will achieve inter-coder reliability. Using the Grounded Theory approach, we will then analyze the agreed upon categories, and place them into themes emerging from discussions.

**D.10. Sample size:** We will enroll 300 adults (150 per intervention group). The primary outcome (Aim 1) is asthma control at Visit 3 (6 months) and Visit 5 (12 months). While a clinically meaningful difference in asthma control within-individual is 0.5, we expect the average difference across groups to be smaller. The WIN Study demonstrated a small difference in mean change of  $0.2 \pm 1.1$  in asthma control across intervention groups at Visit 8 (6 months). The effect was neither clinically nor statistically significant. A difference in mean change of 0.32 in asthma control was found in a study with a different focus, but the effect was not statistically significant, probably due to the small sample size.

**Specific Aim 1:** The power analysis is based on the 2-sample t-test with adjustments for 3 or 5 repeated measures per participant. The adjustment for clustering by patient multiplies the estimated sample size under simple random sampling by a design effect,  $d=1+\rho(n-1)$ , where  $n$ =average number of visits per patient, and  $\rho$  is the patient intraclass correlation. We apply a conservative intraclass correlation of 0.30. The power analysis also takes into consideration the following factors: 1) 18% drop-out as observed in WIN; 2) adjusted 2-sided significance level of 0.025; and 3) 80% power. With these factors, the study is powered to observe a standardized effect of 0.29 and 0.32 difference in mean change in asthma control across intervention groups at 6 months and 12 months, respectively. **Specific Aim 2:** The power analysis examines the intervention effect on 5 asthma outcome measures at 6 and 12 months. Using the same assumptions but with 2-sided  $\alpha=0.005$  to conservatively adjust for multiple comparisons, we will have 80% power to detect a standardized effect of 0.34 and 0.31 between groups at 6 months and 12 months, respectively. **Specific Aim 3:** Power for the economic analysis (costs have greater variability than clinical outcomes) is 81% based on the same effect size, 2-sided  $\alpha$  of 0.05, an effect-cost correlation of -0.1, a difference in cost of \$500 and a willingness to pay (WTP) threshold of \$2500 per year of improved adherence or avoided hospitalization. An increase in the WTP to \$3000 results in 98% power. Thus, the sample size will provide sufficient statistical power for assessment of both clinical and economic evaluations (which requires detecting both effect and cost differences).

**D.11. Data Management:** The Clinical Research Computing Unit will collaborate to finalize CRFs, construct the database, protect its security, perform data entry, review, query and update data; assist with preparation of DSMB reports, and collaborate with biostatisticians as it has for HAP and WIN studies.

**D.12. The Data Safety Monitoring Board** (see Human Subjects) will meet at study start, year 2, and year 5. At these and every 6 months the DSMB will review reports of accrual, baseline comparability between PA and UC groups, adverse events, safety concerns, data quality, maintenance of confidentiality and recommend study modifications and whether the study can continue.

**D.13. Timeline** is summarized in Table 2. Some staff is already identified and trained. We have established relationships at recruitment sites and successful recruitment strategies. The MOP of HAP needs minor modifications. HAP case report forms require small modifications.

**D.14. Anticipated problems:** Insuring recruitment/retention: We will use our successful procedures, using electronic medical records, and relationships developed with practices. We obtain contact information, e.g., cell phone, address, for 3 contacts per participant. Incentives will be given for each DC Visit with the largest at the final visit. We flexibly accommodate meeting times for the convenience of participants. RCs will be diverse, reflecting participant demographics. Guaranteeing a culturally appropriate intervention: RCs will undergo formal training. Co-investigators are also diverse and will in observation of the protocol and in staff meetings guarantee a culturally appropriate approach. Standardizing delivery of PA will be accomplished by the use of procedure manuals; standardized, well-annotated, and carefully constructed case report forms; regular direct observation; and audio-taping of researcher interactions with participants. Assuring physicians do not treat UC participants like PA participants: Physicians will not know which of their patients, if any, are enrolled in the UC arm, only those in PA. Almost all of the intervention takes place between PA and patient or is PA-related so it is unlikely to result in change of provider behavior in the absence of a PA. DCs will ask all subjects post-study if they noted changes in their physician over the study period. Post-study focus groups should add support to this claim. Differences in the impact of the intervention between specialty and primary care practices: will be explored in post-intervention focus groups and in the quantitative analysis of outcomes and mediators.

**D.15. Summary:** This RCT disseminates and implements the PAI to improve asthma outcomes in primary care and specialty practices, in an academic health center, a federally qualified health center, a VA and in English- and Spanish-speaking practices, testing its effectiveness, sustainability, and cost-effectiveness. The real-world individualized PAI is compared to usual care, crafted for a vulnerable population, considers patients' unique contexts, social barriers, and comorbidities and is generalizable to many diseases and medical settings.

